2.2 Secondary Objectives & Endpoints

2.2.1 Evaluate the safety of the combination of romidepsin and lenalidomide.

The endpoint will be the frequency and severity of toxicity events using the NCI CTCAE v 4.03.

2.2.2 Further evaluate efficacy of the combination of romidepsin and lenalidomide.

The endpoints will be progression-free survival (PFS) and overall survival (OS) at 1 and 3 years after start of treatment as well as the duration of response from start of therapy, defined per Cheson criteria.

2.2.3 Evaluate the delay to cytotoxic chemotherapy

The endpoint will be time (in months) to first cytotoxic chemotherapy (TTFCC) from start of treatment.

2.3 Exploratory Objectives & Endpoints

2.3.1 Evaluate the use of NM PET/CT vs CT imaging in PTCL.

The endpoint will be a review of the utilized imaging modalities during treatment as a tool of response assessment. When both imaging modalities are chosen for a patient, response assessment will be compared.

2.3.2 Validate a new prognostic model for newly diagnosed PTCL.[41]

The endpoint will be clinical biomarkers including age, race, histology, and stage as an assessment of prognosis.

2.3.3 Investigate the tumor immunohistochemical profile to identify potential biomarkers associated with prognosis and treatment response.

The endpoint we be comparison of immunohistochemical profiles with treatment outcomes on archived tissue samples.

3.0 Patient Eligibility

The target population for this phase II study is patients with histologically confirmed (previously untreated) peripheral T-cell lymphoma (PTCL). Northwestern University will serve as the lead site and coordinating center for this study. Participating sites will include Weill Cornell Medical College, and City of Hope.

A total of 20 evaluable subjects will be needed for this trial; up to 35 may be accrued to obtain 20 who are evaluable. Approximately 3 potentially eligible patients are seen per month, and it is anticipated that at least 1 per month will be accrued (once all sites are up and running). Potential patients may be referred to the Principal Investigator (PI) at Northwestern University, , or to the local PI at each participating site.

Eligibility will be evaluated by the study team according to the following criteria. Eligibility waivers are not permitted. Subjects must meet all of the inclusion and exclusion criteria to be registered to the study. Study treatment may not begin until a subject is registered. After registration, treatment should begin with 14 days. Please refer to Section 11.4 for complete instructions regarding registration procedures.

3.1 Inclusion Criteria

- 3.1.1 Histologically confirmed diagnosis of PTCL (using the most recent edition of the WHO Classification of Tumors of Hematopoietic and Lymphoid Tissues as guidance) including:
 - Anaplastic large cell lymphoma, ALK-negative
 - Angioimmunoblastic T-cell lymphoma
 - Enteropathy-type T-cell lymphoma
 - Hepatosplenic γδ T-cell lymphoma
 - Peripheral T-cell lymphoma, unspecified (NOS)
 - Transformed mycosis fungoides
 - Subcutaneous panniculitis-like T-cell lymphoma

• Adult T-cell lymphoma/leukemia (ATLL) in need of systemic therapy. NOTE: Patients with adequate archived (well-preserved, formalin-fixed) biopsy tissue remaining will be required to submit a portion for exploratory studies. This is not optional if tissue is available; however, lack of adequate tissue for exploratory studies will not preclude patients from participating.

- 3.1.2 Patients must have bi-dimensionally measurable disease (≥1 cm) by CT imaging. NOTE: Patients with marrow-only disease are eligible; response for these patients will be assessed by repeat bone marrow biopsy.
- 3.1.3 Patients must fit into one of the following categories:
 - Age ≥ 18 years to < 60 years with a cumulative illness rating scale (CIRS) score ≥ 6 OR deemed ineligible for cytotoxic chemotherapy by the treating investigator (see Appendix A for CIRS scoring[42])
 - ≥ 60 years
- 3.1.4 Patients must have adequate organ and marrow function (documented within 14 days prior to registration) as outlined below:

System Laboratory Values				
Hematologic				
ANC	≥ 750/mcl			
Hemoglobin	≥ 8 g/dI			
Platelets	≥ 50,000/mcl			
Hepatic				
Total Bilirubin	≤ 2x upper limit normal (ULN)			
AST (SGOT) and ALT (SPGT)	≤ 3x ULN			
Renal				
Creatinine Clearance	≥ 30 mL/min			
See Appendix D to reference the Cockgroft-Gault equation for				
calculating creatinine clearance.				

- 3.1.5 Patients must have an ECOG performance status ≤ 2 (see Appendix B).
- 3.1.6 All patients must agree to use effective contraception while on study, and all patients must agree to undergo counseling sessions every 28 days about pregnancy precautions and risks of fetal exposure.

Females of childbearing potential (FCBP) must either commit to continued abstinence from heterosexual intercourse or begin TWO acceptable methods of birth control: one highly effective method and one additional effective method AT THE SAME TIME, at least 28 days before starting lenalidomide, during lenalidomide therapy, during dose interruptions, and for at least 28 days following discontinuation of lenalidomide therapy (refer to the patient resources materials or http://www.revlimidrems.com for more information).

Males receiving lenalidomide must agree to use a latex condom during any sexual contact with FCBPs even if they have undergone a successful vasectomy.

NOTE: A FCBP is any woman (regardless of sexual orientation, having undergone a tubal ligation, or remaining celibate by choice) who meets the following criteria:

- Has not undergone a hysterectomy or bilateral oophorectomy
- Has not been naturally postmenopausal for at least 12 consecutive months (i.e., has had menses at any time in the preceding 12 consecutive months).

FCBP should be referred to a qualified provider of contraceptive methods, if needed.

- 3.1.7 FCPB must have a negative urine or serum pregnancy test within 7 days prior to registration, and be willing to adhere to the scheduled pregnancy testing as required in the Revlimid REMS® program. NOTE: Should a woman become pregnant or suspect she is pregnant while participating in this study, she should inform her treating physician immediately.
- 3.1.8 Patients must be free of any prior malignancies for ≥1 year at the investigator's discretion.

NOTE: The exception to this would be currently treated squamous cell and basal cell carcinoma of the skin, carcinoma in situ of the cervix, breast, or bladder, or surgically removed melanoma in situ of the skin (stage 0) with histologically confirmed free margins of excision.

3.1.9 All study participants must be registered into the mandatory Revlimid REMS® program, and be willing and able to comply with the requirements of REMS®.

3.1.10 Patients must have the ability to understand and the willingness to sign a written informed consent prior to registration.

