6.2.1 Complete Remission (CR)

CR requires the following:

Complete disappearance of all detectable clinical evidence of disease and disease-related symptoms if present before therapy.

1. Typically FDG-avid lymphoma: in patients with no pretreatment PET scan or when the PET scan was positive before therapy, a post-treatment residual mass of any size is permitted as long as it is PET negative.

Variably FDG-avid lymphomas/FDG avidity unknown: in patients without a pretreatment PET scan, or if a pretreatment PET scan was negative, all lymph nodes and nodal masses must have regressed on CT to normal size (\leq 1.5 cm in their greatest transverse diameter for nodes > 1.5 cm before therapy). Previously involved nodes that were 1.1 to 1.5 cm in their long axis and more than 1.0 cm in their short axis before treatment must have decreased to \leq 1.0cm in their short axis after treatment.

- 2. The spleen and/or liver, if considered enlarged before therapy on the basis of a physical examination or CT scan, should not be palpable on physical examination and should be considered normal size by imaging studies, and nodules related to lymphoma should disappear. However, determination of splenic involvement is not always reliable because a spleen considered normal in size may still contain lymphoma, whereas an enlarged spleen may reflect variations in anatomy, blood volume, the use of hematopoietic growth factors, or causes other than lymphoma.
- 3. If the bone marrow was involved by lymphoma before treatment, the infiltrate must have cleared on repeat bone marrow biopsy. The biopsy sample on which this determination is made must be adequate (with a goal of > 20 mm unilateral core). If the sample is indeterminate by morphology, it should be negative by immunohistochemistry. A sample that is negative by immunohistochemistry but that demonstrates a small population of clonal lymphocytes by flow cytometry will be considered a CR until data become available demonstrating a clear difference in patient outcome.

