6.2.2 Partial Response (PR)

PR requires the following:

- At least a 50% decrease in sum of the product of the diameters (SPD) of up to six of the largest dominant nodes or nodal masses. These nodes or masses should be selected according to all of the following: they should be clearly measurable in at least 2 perpendicular dimensions; if possible they should be from disparate regions of the body; and they should include mediastinal and retroperitoneal areas of disease whenever these sites are involved.
- 2. No increase should be observed in the size of other nodes, liver, or spleen.

- 3. Splenic and hepatic nodules must regress by ≥ 50% in their SPD or, for single nodules, in the greatest transverse diameter.
- 4. With the exception of splenic and hepatic nodules, involvement of other organs is usually assessable and no measurable disease should be present.
- 5. Bone marrow assessment is irrelevant for determination of a PR if the sample was positive before treatment. However, if positive, the cell type should be specified (e.g., large-cell lymphoma or small neoplastic B-cells). Patients who achieve a CR by the above criteria, but who have persistent morphologic bone marrow involvement will be considered partial responders. When the bone marrow was involved before therapy and a clinical CR was achieved, but with no bone marrow assessment after treatment, patients should be considered partial responders.
- 6. No new sites of disease should be observed.
- 7. Typically FDG-avid lymphoma: for patients with no pretreatment PET scan or if the PET scan was positive before therapy, the post-treatment PET should be positive in at least one previously involved site.

Variably FDG-avid lymphomas/FDG-avidity unknown: for patients without a pretreatment PET scan, or if a pretreatment PET scan was negative, CT criteria should be used.

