6.2.4 Relapsed Disease (after CR) or Progressive Disease (after PR or SD)

- Lymph nodes should be considered abnormal if the long axis is more than 1.5 cm regardless of the short axis. If a lymph node has a long axis of 1.1 to 1.5 cm, it should only be considered abnormal if its short axis is more than 1.0. Lymph nodes ≤ 1.0 x ≤ 1.0 cm will not be considered as abnormal for relapse or progressive disease.
- 2. Appearance of any new lesion more than 1.5 cm in any axis during or at the end of therapy, even if other lesions are decreasing in size. Increased FDG uptake in a previously unaffected site should only be considered relapsed or progressive disease after confirmation with other modalities. In patients with no prior history of pulmonary lymphoma, new lung nodules identified by CT are mostly benign. Thus, a therapeutic decision should not be made solely on the basis of the PET without histologic confirmation.
- 3. At least a 50% increase from nadir in the SPD of any previously involved nodes, or in a single involved node, or the size of other lesions (e.g., splenic

or hepatic nodules). To be considered progressive disease, a lymph node with a diameter of the short axis of less than 1.0 cm must increase by \geq 50% and to a size of 1.5 x 1.5 cm or more than 1.5 cm in the long axis.

- 4. At least a 50% increase in the longest diameter of any single previously identified node more than 1 cm in its short axis.
- 5. Lesions should be PET positive if observed in a typical FDG avid lymphoma or the lesion was PET positive before therapy unless the lesion is too small to be.

Response	Definition	Nodal Masses	Spleen, Liver	Bone Marrow
CR	Disappearance of all evidence of disease	 (a) FDG-avid or PET positive prior to therapy; mass of any size permitted if PET negative (b) Variably FDG-avid or PET negative; regression to normal size on CT 	Not palpable, nodules disappeared	Infiltrate cleared on repeat biopsy; if indeterminate by morphology, immunohistochemistry should be negative

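### Section 3.1.2 admits nodes so small that Section 6.2.1 sets them no CT shrinkage target, so an unchanged scan can be read as nodal CR or as SD

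*Combined protocol and SAP*

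**What the plan says.** **Entry.** Section 3.1.2: "Patients must have bi-dimensionally measurable disease (≥1 cm) by CT imaging". The wording covers disease in general, sets no minimum for nodes, and does not say whether 1 cm applies to both diameters or only to the longer one. Marrow-only disease is also eligible.

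**CR on CT.** Section 6.2.1 applies its CT branch to variably FDG-avid lymphoma or unknown avidity, when there was no pretreatment PET or it was negative. There, "all lymph nodes and nodal masses must have regressed on CT to normal size". Explicit targets follow for two groups only: nodes above 1.5 cm before therapy, and "Previously involved nodes that were 1.1 to 1.5 cm in their long axis and more than 1.0 cm in their short axis before treatment".

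**Abnormal nodes.** Section 6.2.4, item 1, says of a node with long axis 1.1-1.5 cm that "it should only be considered abnormal if its short axis is more than 1.0" (cm). It adds: "Lymph nodes ≤ 1.0 x ≤ 1.0 cm will not be considered as abnormal for relapse or progressive disease".

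**PR and SD.** Section 6.2.2 requires "At least a 50% decrease in sum of the product of the diameters (SPD"). Section 6.2.3 makes SD the category for patients who reach neither CR nor PR and do not progress. On its CT branch, SD is described by lesions that have not changed in size.

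**Use.** ORR is the primary endpoint (Sections 2.1 and 10.1), with 20 evaluable patients. Section 7.4 stops the trial if 6 or fewer of the first 12 respond at 3 months. PET is encouraged but optional (Table 4, footnotes 2 and 12), so CT-only assessment can occur.

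**The concern.** A response rate is meant to count tumour shrinkage. That requires the disease that qualifies a patient for entry to lie above the size the response criteria regard as normal. Here the two limits overlap: some nodes count as measurable disease at entry yet already satisfy the size limits used to define nodal CR.

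For a patient with only such nodes, the response category at cycle 3 may depend on how the assessor reads the text. The error can run only one way, because a patient with no change can be moved into the responder group but a true responder is not moved out. With 20 patients in the final estimate and 12 at the interim look, single classifications matter. Section 3.0 permits no eligibility waivers, so the written threshold decides entry, and the documents describe no central review of scans.

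**Working it through.** **1. The plan's own precision figure.** Section 10.1: 1.96 x 0.5/sqrt(20) = 0.219, stated as 0.22. It reproduces, and serves below as a yardstick.

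**2. Where entry and response limits overlap.** Applying 3.1.2, 6.2.1 (CT branch) and 6.2.4 item 1 to individual nodes, with PR requiring the SPD to fall to half or less:

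| Node (cm) | SPD (cm²) | PR needs SPD at most | Abnormal under 6.2.4 | CR target in 6.2.1 |
|---|---|---|---|---|
| 1.0 x 1.0 | 1.00 | 0.50 | no | none |
| 1.2 x 1.0 | 1.20 | 0.60 | no | none |
| 1.5 x 1.0 | 1.50 | 0.75 | no | none |
| 1.4 x 1.1 | 1.54 | 0.77 | yes | short axis ≤1.0 |
| 1.6 x 1.0 | 1.60 | 0.80 | yes | diameter ≤1.5 |

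- If 1 cm applies to both diameters, the overlap on a 1 mm grid is six sizes, 1.0 x 1.0 to 1.5 x 1.0 cm. The short axis must be exactly 1.0 cm.
- If it applies to the long axis only, the overlap is every node with long axis 1.0-1.5 cm and short axis 1.0 cm or less.
- Long axes strictly between 1.0 and 1.1 cm are not expressly classified in 6.2.4.

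**3. An unchanged 1.5 x 1.0 cm node.** It fails PR (SPD 1.50, needs 0.75). It fits the CT description of SD. It also lies within the size limits for nodal CR, and because SD presupposes that CR was not reached, the SD wording does not settle the matter.

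**4. A 1.4 x 1.1 cm node.** Moving the short axis from 1.1 to 1.0 cm takes the SPD from 1.54 to 1.40, a fall of 0.14/1.54 = 9.1%. That meets the nodal CR target, although PR asks for 50%.

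**5. Effect on ORR.** Let k patients of this kind be scored as responders, with true response rate p. The expected inflation is k(1 - p)/20.
- p = 0.50 (assumed): 0.5/20 = 2.5 points per patient.
- p = 0.25 (assumed): 0.75/20 = 3.75 points per patient.
- Ceiling, if the patient would certainly not have responded: 1/20 = 5 points.

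The documents do not give k.

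**6. Effect on the interim look, as an upper bound.** Passing needs at least 7 of 12. If k of the 12 are certain responders, the probability of passing is P(X ≥ 7 - k) with X binomial on 12 - k patients:

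| Assumed p | k = 0 | k = 1 | k = 2 |
|---|---|---|---|
| 0.50 | 1586/4096 = 0.387 | 1024/2048 = 0.500 | 638/1024 = 0.623 |
| 0.25 | 0.014 | 0.034 | 0.078 |

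These figures assume that every such patient is scored as a responder, which the text does not require.

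**The case against.** A reader might infer that such a patient is an automatic complete responder. The documents do not support that. Section 6.2.1 also requires every clinical sign of disease and any disease-related symptom to be gone, and involved marrow to have cleared. It speaks of nodes having regressed, and an unchanged node has not. Section 6.2.3 offers SD for the same scan. This objection stands: the text is ambiguous between SD and CR, and does not dictate CR.

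The affected group is also narrow. All of the patient's measurable disease must be nodes of this size, and response must be read on the CT branch. If both diameters must reach 1 cm, only the boundary short axis of 1.0 cm is involved. Encouraging PET narrows the group further. This stands too, and limits how often the gap matters.

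Finally, item 1 of 6.2.4 sits under relapse and progression, and its sentence on the smallest nodes is limited to those outcomes. It does not define baseline involvement. That is correct, but the gap for CR does not depend on it: 6.2.1 itself sets no target for these nodes.

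**Conclusion.** The mismatch is real and open to a simple remedy. It makes the response category ambiguous for a small, uncounted group, with a possible upward bias in ORR. At an assumed true rate of 50%, the expected inflation is about 2.5 points per patient so scored, and never more than 5, against a confidence-interval half-width of 22 points.

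Two stronger readings go too far. Charging a full 5 points per patient assumes that each would otherwise certainly have failed to respond. Saying that the gap carries the trial past its futility rule assumes certain responders among the first 12, and nothing in the documents establishes that there are any. Nor do the documents give a CT measurement error, so whether a 1 mm change is noise cannot be settled from them. What can be said is that 1 mm is enough.

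**What to change.** 1. **Section 3.1.2.** For patients qualifying on nodal disease, require at least one node with long axis above 1.5 cm or, at minimum, one node abnormal under 6.2.4. Leave marrow-only and extranodal eligibility as they are. Either version ensures that the qualifying node has a CR shrinkage target. The minimum version still admits the 1.4 x 1.1 cm node. Neither removes boundary effects altogether: a 1.6 cm node also needs only 1 mm to reach 1.5 cm.
2. **Section 6.2.** State that a patient with no baseline node above the chosen threshold cannot be scored CR on nodal CT size alone without a measured decrease.
3. **Patients already enrolled.** Keep them in the primary ORR under the evaluability rule in Section 4.6. Removing them would conflict with that rule and would be a post hoc exclusion in an open-label trial. Report a sensitivity ORR without patients whose only baseline disease is sub-threshold nodes. Do not apply the nodal rule to extranodal-only or marrow-only patients.

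**Cost.** One line in 3.1.2, one in 6.2, and one extra summary using the baseline CT already required. A few patients with very small-volume nodal disease would become ineligible.

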3.2 Exclusion Criteria

- 3.2.1 Patients with a diagnosis of any of the following are not eligible:
 - Anaplastic large cell lymphoma, ALK-positive
 - Anaplastic large-cell lymphoma, primary cutaneous type
 - Precursor T-lymphoblastic lymphoma/leukemia
 - Mycosis fungoides/Sezary syndrome (except transformed MF)
 - NK-cell leukemia
 - T-cell granular lymphocytic leukemia
 - T-cell prolymphocytic leukemia.
- 3.2.2 Patients must not have received prior systemic therapy for PTCL (except for corticosteroids, which are permitted to treat lymphoma for 10 or fewer days at any dose; no washout period required in this case as long as they discontinue prior to starting study therapy).

NOTE: Corticosteroids are permitted on study for treatment of any condition other than PTCL.

NOTE: Topical treatment may have been given for prior existence of cutaneous lymphoma that has since become systemic PTCL. However, these topical therapies should be stopped at time of registration.

- 3.2.3 Patients who received chemotherapy (including monoclonal antibodies) or radiotherapy, administered for any condition, ≤28 days prior to registration are not eligible.
- 3.2.4 Patients who have received any other HDAC inhibitors or IMID agents for any reason are not eligible.
- 3.2.5 Patients receiving ongoing treatment with any other investigational agents are not eligible.
- 3.2.6 Patients receiving concurrent immunosuppressive medications post-transplant (at the time of registration) are not eligible.
- 3.2.7 Patients with known CNS (central nervous system) involvement of lymphoma are not eligible.
- 3.2.8 Patients who have an uncontrolled intercurrent illness including, but not limited to any of the following are not eligible:
 - ongoing or active infection
 - symptomatic congestive heart failure
 - unstable angina pectoris
 - cardiac arrhythmia
 - psychiatric illness/social situations that would limit compliance with study requirements.
- 3.2.9 Patients with a known HIV infection are not eligible.
- 3.2.10 Patients who are pregnant or actively nursing an infant are not eligible.
- 3.2.11 Patients with a QT interval > 480 msec (using the Bazett's formula) ≤28 days prior to registration are not eligible.

4.0 Treatment Plan

Patients will be treated in cycles of 28 days (±3 days). Patients will receive romidepsin (at a dose of either 10 or 14 mg/m² – see 4.1.1 for details) IV on days 1, 8, and 15 as well as lenalidomide 25 mg PO daily on days 1- 21 of each cycle. Treatment may continue for one year or until disease progression or unacceptable toxicity. Patients who do not achieve a response of PR or better should continue to be treated only if they have SD (i.e., not PD), and if they do not have other options available that would present a more favorable risk/benefit ratio. Clinical suspicion of progressive disease (PD) or loss of response should be investigated radiographically (or by repeat bone marrow biopsy for marrow-only disease), and if confirmed, will result in removal from active therapy; such patients will remain in study follow up. In this case, it is strongly recommended that investigators consider early initiation CHOP or similar chemoimmunotherapy (off trial).

Treatment will be based on weight at baseline. Dosing should only be modified if the patient's weight has changed by more than 10% from baseline or the BSA has changed more than 5%.

It is intended that all treatments will be administered on an outpatient basis. However, treatment can be initiated during hospitalization (i.e., for newly-diagnosed patients), and can continue during unforeseen hospitalizations, but only at the discretion of the local primary investigator (PI).

